**Table 2: Outcomes and Measures**

Primary Outcome	Measures	Variable Type	How Collected	Time Point
Number of Diabetes Care Gaps through 12 Months	Number of diabetes care gaps per patient out of four possible: 
 
no diabetes eye exam in the last 12 months,
 
no hemoglobin A1C blood test in the last 6 months,
 
no urine microalbumin in the last 12 months, and
 
no pneumococcal vaccination of any kind (i.e., never received PPSV-23, PCV-13, PCV-15, or PCV-20)
 
	Ordinal	EHR abstraction	T 0 - T 3
Secondary Outcomes				
Number of Diabetes Care Gaps at 6 Months	Number of diabetes care gaps per patient out of four possible: 
 
no diabetes eye exam in the last 12 months,
 
no hemoglobin A1C blood test in the last 6 months,
 
no urine microalbumin in the last 12 months, and
 
no pneumococcal vaccination of any kind (i.e., never received PPSV-23, PCV-13, PCV-15, or PCV-20)
 
	Ordinal	EHR abstraction	T 0 - T 3
Attitudes toward Managing Diabetes in General	Items adapted from the Manage Disease in General Scale of the Chronic Disease Self-Efficacy Scales.	Continuous	Questionnaire	T 0 - T 3
Diabetes self-efficacy	Perceived Diabetes Self-Management Scale (PDSMS)	Continuous	Questionnaire	T 0 - T 3
Understanding of Diabetes Monitoring and Preventative Care	Unique study specific items to assess participants' understanding of recommended diabetes monitoring and preventative care	Categorical	Questionnaire	T 0 - T 2
Diabetes distress	Problem Areas in Diabetes Scale (PAID-5)	Continuous	Questionnaire	T 0 - T 3
Satisfaction with MHAV	System Usability Scale and user experience questions	Continuous	Questionnaire	T 0 - T 3
Patient-initiated orders	# of patient-initiated orders for evidence-based diabetes monitoring & preventative services (e.g., A1c)	Continuous	EHR Abstraction, Tableau & Clarity Servers	T 0 - T 3

Reported completion outside VUMC system	# of reports diabetes eye exams outside the VUMC system in response to the To-Do item received via the intervention  # of reports of outside diabetes eye exam that meet criteria for screening for diabetic eye disease.	Continuous	EHR Abstraction, Tableau & Clarity Servers	T 0 - T 3
Blood glucose control	Hemoglobin A1C	Continuous	EHR abstraction	T 0 - T 3
Treatment intensification	Addition of: a. antihyperglycemic medications b. antihypertensive medications	Categorical	EHR abstraction	T 0 - T 3

T0 = baseline, T1 = 3-month follow-up, T2 = 6-month follow-up, and T3 = 12-month follow-up

Secondary intermediate outcomes include attitudes toward managing diabetes in general, diabetes self-efficacy, understanding of diabetes monitoring and preventative care, diabetes distress, satisfaction with MHAV, patient-initiated orders, and reported completion outside VUMC system. Additional secondary outcomes, blood glucose control and treatment intensification, will also be assessed by EHR abstraction.

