Patients reporting an outside eye exam will be contacted by study staff and asked to complete an Authorization for Release of Medical Information to VUMC via REDCap. If the patient agrees and signs the release, trained study staff will request the records accordingly. Once the eye exam records are received, trained study staff will review the records to determine if the records document screening for diabetic eye disease (i.e., was the participant's self-report of a diabetes eye exam accurate). If the eye exam records do not indicate screening for diabetes related eye disease (i.e., a diabetes eye exam), KSP will contact the participant by phone with this information and encourage the participant to call their eye doctor to schedule a diabetes eye exam. If the participant prefers, the participant will be invited to schedule a diabetes eye exam at Vanderbilt Eye Institute. If the participant can't be reached by phone, they will be sent a letter with this information. Any outside eye exam records received will be scanned into the participant's VUMC medical record and their primary care physician will be notified.

[Data Collection and Outcome Measures.](#) Study participants will complete questionnaires electronically via email using REDCap™ at four time points: enrollment/baseline (T0), 3-month follow-up (T1), 6-month follow-up (T2), and 12-month

follow-up (T3). Participants will complete an enrollment/baseline questionnaire (T0) including basic demographic questions, items about computer and internet use, health literacy, numeracy, and eHealth literacy. Based on prior experience, we estimate time to completion for each questionnaire to be about 20 minutes. Participants will be compensated \$40 each for completing questionnaires (\$160 total if they complete all four).

The primary outcome measure will be the number of diabetes care gaps out of the four selected DM monitoring & preventative services through 12-months follow-up.

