## 6.0 Statistical Analysis Plan

We will use descriptive statistics to characterize the study participants and the primary and secondary outcomes. For the primary analysis, an ordinal mixed effects regression model will be used. For dichotomous outcomes, a logistic mixed effects regression model will be used. For continuous outcomes, a multivariate mixed effects regression model will be used. If there is imbalance, we will control for baseline patient level covariates, including socioeconomic status, marital status, race/ethnicity, education level, age, sex, health literacy, technology use, and diabetes distress. We will allow for nonlinear associations by modeling continuous covariate with restricted cubic splines when needed. Similar models will be used for all the secondary outcomes except for HbA1c. Due to the frequency of HbA1c measurements, we will use a linear regression model as opposed to a mixed effects model with the HbA1c value at the 12-month timepoint as the dependent variable. Appropriate statistical methods, such as multiple imputation, will be used where missing data are present.

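### The plan does not define the arm contrast for the 12-month primary or 6-month secondary gap count, nor how the baseline count enters the model

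*Combined protocol and SAP*

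**What the plan says.** Section 5.0 (Data Collection and Outcome Measures) defines the primary as a count over the "four selected DM monitoring & preventative services through 12-months follow-up". Table 2 names it "Number of Diabetes Care Gaps through 12 Months" and adds a secondary, "Number of Diabetes Care Gaps at 6 Months". Both rows begin "Number of diabetes care gaps per patient out of four possible", then list the same four items (eye exam, A1c, urine microalbumin, pneumococcal vaccination) with the same look-backs. Both are ordinal, both come from EHR abstraction, and both have the Time Point entry T0 to T3. The table footnote makes T2 the 6-month and T3 the 12-month follow-up.

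On analysis, Section 6.0 says: "For the primary analysis, an ordinal mixed effects regression model will be used". For the rest: "Similar models will be used for all the secondary outcomes except for HbA1c". HbA1c instead gets a linear regression on its 12-month value, and the reason given is how often it is measured. Baseline covariates are to be controlled only if there is imbalance, and the gap count is not among those named.

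**The concern.** An outcome at 6 months cannot have a time point that runs to 12 months, so at least one cell of Table 2 is wrong or loosely used. That would be minor if the SAP settled the matter, but it does not. It leaves open which visits are outcome rows, what the T0 count is for, whether the model has time and arm-by-time terms, and which coefficient is the primary result.

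Two things are at stake. First, several analyses fit the text and estimate different quantities: arm status at T3, an average over T1-T3, or an average that includes T0. A choice among them after the data are seen would weaken the primary result. Second, T0 precedes the intervention, so the true arm difference there is zero by randomisation. A model that averages over T0 understates the effect.

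The roles of T0 and time matter in this trial because one recruitment route in Section 5.0 identifies patients who already have open care gaps. Counts may then change over time in both arms, whatever the intervention does.

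**Working it through.** The plan has no figure to reproduce. The target of 500 (250 per arm, Section 4.0) is given without alpha, power, effect size or outcome distribution. The check is therefore a comparison of the text, followed by arithmetic on the one specification that would cause harm.

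**Text side by side**

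1. The two gap-count rows of Table 2 differ in name (12 months, 6 months) and agree in items, variable type, source and Time Point (T0-T3).
2. The Time Point column is not uniform: the row on understanding of diabetes monitoring reads T0-T2. The entries were varied where that was meant.
3. The column is not always the analysis window either: HbA1c reads T0-T3, yet Section 6.0 analyses only its 12-month value.
4. The HbA1c exception is justified by measurement frequency and set against a mixed model. This implies that the other mixed models use repeated visits within patient. HbA1c is the only outcome for which Section 6.0 names an analysis time.

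The table alone therefore does not fix the contrast, and the SAP does not supply it.

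**What happens if T0 is an outcome row and only an arm main effect is fitted**

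Assumptions, not in the documents: linear scale, random intercept, all four visits observed for everyone. The visits then carry equal weight. Write d0 to d3 for the arm differences at T0 to T3, with d0 = 0 by randomisation.

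Arm coefficient = (d0 + d1 + d2 + d3)/4 = (3/4) × (d1 + d2 + d3)/3

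The coefficient is 0.75 of the T1-T3 average, whatever the shape of the effect. Three assumed profiles, scaled so that the T3 effect is 1:

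- Constant (0, 1, 1, 1): pooled 0.75, T1-T3 average 1.00, ratio 0.75.
- Ramp (0, 1/3, 2/3, 1): pooled 0.50, T1-T3 average 0.67, ratio 0.75.
- Late (0, 0, 0.5, 1): pooled 0.375, T1-T3 average 0.50, ratio 0.75.

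The ratio to the T3 effect does vary (0.75, 0.50, 0.375). It combines two things: the 0.75 from including T0, and the gap between a T1-T3 average and a T3 status. The second is a choice of estimand and not dilution.

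**What the alternatives do**

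With an arm-by-time term, the contrast at T2 or T3 is d2 or d3, and T0 does not shrink it. The same holds if T0 is a covariate, or if it is an outcome with one common mean for both arms.

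Conditioning on T0 also affects precision. Assume unit variance and a correlation r between any two visits. Relative variances of the arm contrast are:

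- T3, unadjusted: 1
- T3, adjusted for T0: 1 − r²
- T1-T3 average, adjusted for T0: (1 + 2r)/3 − r²

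For r = 0.3, 0.5 and 0.7, adjusted T3 gives 0.91, 0.75 and 0.51. The adjusted average gives 0.44, 0.42 and 0.31. Adjustment lowers the variance of the T3 contrast by 9%, 25% and 49%. The average is more precise than T3 alone, but when the effect builds up it estimates a smaller quantity.

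**The case against.** The strongest reply is that nothing here is an error in the analysis, only brevity. The Time Point column may list the collection schedule, as it evidently does for HbA1c. The outcome names already give different horizons. A competent analyst would fit visit-specific contrasts, and the text does not exclude an arm-by-time term.

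Much of this stands, and it rules out two stronger readings that a reader might infer. One is that the 6-month secondary duplicates the primary. That follows only if the column overrides the outcome's own name, and the HbA1c row shows that the column cannot be read that way throughout. The other is that the planned analysis pools pre-treatment data and dilutes the effect. Section 6.0 nowhere specifies an arm main effect over T0-T3, so dilution is a possible result of an incomplete specification and not a feature of the plan.

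It is also fair to say that T0 may properly be an outcome row if its mean is constrained equal across arms, and that choosing between T3 status and a T1-T3 average is the sponsor's decision.

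What the reply does not answer is that the 6-month cell conflicts with its label, and that a T3 contrast or baseline adjustment for the gap count has to be supplied by the reader.

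**Conclusion.** The concern holds as a gap in specification. The conflict in the 6-month row, and the absence of an analysis visit, an arm contrast and a role for the T0 count, are established by reading and need no assumptions. The size of the harm is conditional. It is a shrinkage to about 0.75 of the T1-T3 average effect if T0 is an outcome row under an arm main effect only, and no shrinkage from T0 under an arm-by-time contrast or baseline adjustment. The 0.75 rests on a linear scale, equal weighting and balanced visits. For the planned ordinal model it is a guide only. The variance figures rest on an assumed common correlation. The documents give no inputs from which a loss of power could be stated. The change should be made because it is nearly free, closes the route to dilution and usually adds precision.

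**What to change.** 1. Condition the primary and 6-month gap-count models on the T0 gap count in every case, not only on imbalance. Enter it as a prespecified covariate, or as a baseline mean constrained equal across arms.
2. Include arm, time and arm-by-time terms. Define the 6-month secondary as the arm odds ratio at T2, and correct its Time Point cell in Table 2 to match.
3. State the primary contrast. The arm odds ratio at T3 fits a 12-month status. If the sponsor means an average over T1-T3, say so and leave T0 out of the average. Align the outcome name and Time Point cell with the choice.
4. Anchor the T2 and T3 look-backs to fixed times after randomisation. Table 2 does not say from which date they are counted.

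The cost is two table cells and a few SAP sentences. Table 2 already schedules the T0 count from the EHR, so no new data are needed. The one real downside is that a T3 contrast can be less precise than a T1-T3 average, which the sponsor should weigh when choosing the primary contrast.

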## 6.0 Statistical Analysis Plan

We will use descriptive statistics to characterize the study participants and the primary and secondary outcomes. For the primary analysis, an ordinal mixed effects regression model will be used. For dichotomous outcomes, a logistic mixed effects regression model will be used. For continuous outcomes, a multivariate mixed effects regression model will be used. If there is imbalance, we will control for baseline patient level covariates, including socioeconomic status, marital status, race/ethnicity, education level, age, sex, health literacy, technology use, and diabetes distress. We will allow for nonlinear associations by modeling continuous covariate with restricted cubic splines when needed. Similar models will be used for all the secondary outcomes except for HbA1c. Due to the frequency of HbA1c measurements, we will use a linear regression model as opposed to a mixed effects model with the HbA1c value at the 12-month timepoint as the dependent variable. Appropriate statistical methods, such as multiple imputation, will be used where missing data are present.

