Participants and Recruitment. Potential participants will be identified automatically using VUMC's *Subject Locator* to query the EHR for patients with upcoming clinic appointments who meet the discrete inclusion and exclusion criteria. In addition, VUMC population health and quality improvement initiatives have created a report that identifies established patients with diabetes who receive care at the primary care clinics participating in the study and have current diabetes care gaps (e.g., no diabetes eye exam in the last year). These patients are the target population for study (i.e., Vanderbilt primary care patients with diabetes) and as such these patients are potentially eligible to participate in the study. With approval of the clinic director, we will send potentially eligible patients a recruitment letter describing the study and providing them with the contact information (study phone number and e-mail address) for IRB-approved study personnel. If after receiving the letter, a patient is interested in the study, they may contact study personnel to learn more and consider participating in the study. The recruitment letter will also include a QR code and URL link to a REDCap site where interested patients can review eligibility criteria, review the consent form, and enroll. Within each step of this REDCap process, we have emphasized (i.e., underlined) statements encouraging potential participants to call or email study staff with any questions or concerns at any time and provide the study's phone number and e-mail address. For self-initiated consent, the study contact information is provided (email and phone) for prospective participants to contact trained study personnel with questions, prior to consent. Trained key study personnel will also contact patients after receiving the completed REDCap informed consent document to provide another opportunity to ask questions, confirm eligibility, and onboard the patient to the study. Patients who do not respond to the recruitment letter may be contacted by phone to ensure they received the letter and offer them information about the study.

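### The primary model is adjusted only on an undefined imbalance, and the plan does not commit to using the baseline care-gap count

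*Combined protocol and SAP*

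**What the plan says.** Section 6.0 is the whole analysis plan. On the primary outcome it says "For the primary analysis, an ordinal mixed effects regression model will be used". It does not give the fixed effects, the random effects or the time points that form the response. After naming the model types it adds "If there is imbalance, we will control for baseline patient level covariates". Nine characteristics are then named, in a list that reads "including socioeconomic status, marital status, race/ethnicity, education level, age, sex, health literacy, technology use, and diabetes distress". The plan gives no test, threshold, set of variables to inspect, timing or decision maker. It does not say whether a trigger brings in all nine named covariates or only the unbalanced ones.

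The baseline gap count is not among the nine. The list is introduced as examples, so the count is not excluded either.

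Table 2 gives the primary outcome as "Number of Diabetes Care Gaps through 12 Months", ordinal, abstracted from the EHR over T0 to T3, with T0 defined as baseline. A separate secondary outcome, "Number of Diabetes Care Gaps at 6 Months", points to 12 months as the primary time. Nothing says whether T0 is a covariate, part of the response, or unused.

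Section 4.0 describes permuted blocks with no stated stratification factor, so balance on the T0 count is not stated to be secured by design.

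**The concern.** The T0 count is the baseline value of the primary outcome and is already planned for collection. Adjusting for it in every case would use whatever it predicts about the 12-month count. Adjusting only when the arms look different uses that information in some randomizations and not in others.

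Some correlation between T0 and 12 months is built into the outcome. One component is "no pneumococcal vaccination of any kind", so a patient vaccinated by T0 can never show that gap later.

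Two things are at stake: a primary model that is not fixed before the data are compared by arm, and some power. Validity of the test is not at stake.

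**Working it through.** **The plan's own figure.** The target of 500 (250 per arm) cannot be reproduced. The documents give no alpha, power, effect size, outcome distribution or baseline correlation. Everything below is illustrative.

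**Inputs.** From the documents: 250 per arm (Section 4.0), the four gap definitions (Table 2), and a 40% eye-exam gap (Section 1.0). Assumed: baseline gaps of 35% for microalbumin, 30% for A1c and 30% for vaccine; 4% of patients vaccinated per quarter; two-sided alpha 0.05; and an effect giving about 78% unadjusted power (marginal odds ratio 0.63–0.64). Care events are simulated by quarter. Patient heterogeneity is varied to span a range of T0-to-T3 correlation r, where T3 is 12 months.

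**Step 1: value of T0.** Power of a proportional-odds model of the T3 count (5,000 replicates):

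| r | T0 unused | T0 always | T0 if p<0.05 on T0 | T0 if standardized difference on T0 >0.10 |
|---|---|---|---|---|
| 0.20 | 79.4% | 81.5% | 79.7% | 80.2% |
| 0.33 | 80.0% | 84.9% | 80.6% | 82.2% |
| 0.45 | 77.0% | 86.6% | 78.0% | 81.0% |

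The gains from always using T0 are 81.5 − 79.4 = 2.1, 84.9 − 80.0 = 4.9 and 86.6 − 77.0 = 9.6 points.

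Closed-form check from 78% power: Φ(2.732/√(1−r²) − 1.96) gives 78.5, 79.6, 83.1 and 86.4% at r = 0.11, 0.20, 0.35 and 0.45. A separate simulation with a linear-score test moved power from 78.7 to 80.0%, 77.5 to 80.5% and 74.3 to 82.7% at r = 0.20, 0.30 and 0.43. Both agree in direction and rough size.

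One recruitment source is patients who "have current diabetes care gaps". If every patient had at least one gap at T0, power would go from 78.1 to 78.7% at r = 0.17 (0.6 points), from 79.6 to 81.2% at 0.19, from 79.0 to 84.2% at 0.36, and from 78.8 to 87.6% at 0.45.

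**Step 2: what a trigger on T0 alone keeps.** Divide the rule's gain by the full gain.
- p<0.05: 0.3/2.1, 0.6/4.9 and 1.0/9.6, or 14, 12 and 10%.
- Standardized difference >0.10: 0.8/2.1, 2.2/4.9 and 4.0/9.6, or 38, 45 and 42%.

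Unrounded powers give 10–16% and 39–45%.

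**Step 3: how often nine covariates would trigger adjustment.** The standard error of a standardized difference is √(2/250) = 0.0894. The chance p of crossing the threshold on one covariate is 0.0253 (>0.20), 0.05, 0.10 or 0.2636 (>0.10). With nine independent covariates, 1 − (1−p)⁹ is 0.206, 0.370, 0.613 and 0.936.

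**Step 4: what an any-covariate trigger keeps, if it brings in all covariates including T0.** With q from Step 3 and k from Step 2, retention is q + (1−q)k.
- p<0.05: 0.370 + 0.630 × 0.10 to 0.370 + 0.630 × 0.16 = 43% to 47%.
- Standardized difference >0.10: 0.936 + 0.064 × 0.39 to 0.936 + 0.064 × 0.45, about 96%.

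At >0.20, k was not computed. The first term alone is 21%, so a stricter threshold can fall below this range.

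**Step 5: validity.** Under the null, the rules applied to T0 rejected in 3.7–5.5% of trials. A continuous-score approximation gave 4.7, 4.4 and 3.3% for the p<0.05 rule at correlations of 0.3, 0.5 and 0.7. Neither shows material inflation.

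**The case against.** The strongest case on the other side has four parts.

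**The plan may already use T0.** Section 6.0 names a mixed model and sets HbA1c apart as the outcome that gets a single 12-month regression instead. With Table 2's T0-to-T3 span, this suggests repeated gap counts in one model, possibly with T0 as a response. This stands as a limit on size. Step 1 compares 12-month-only models, and the gain over the planned mixed model has not been shown. In one smaller run at r = 0.33 (450 data sets), the 12-month-only gain was 84.0 − 81.8 = 2.2 points rather than 4.9, a difference that may be simulation noise. It does not remove the point, because the text never states T0's role.

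**The rule may fire often.** A reader might infer that conditional adjustment gives up most of the available precision. That holds only if T0 imbalance alone is the trigger. If any covariate can trigger adjustment for all, Step 4 shows nearly all of the gain may be kept. The documents do not say which is meant.

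**Nothing is invalid.** A reader might infer that choosing the model on observed balance biases the result or inflates type I error. The calculations do not support that.

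**Adjustment has a price.** In a proportional-odds model it changes the target from a marginal to a conditional odds ratio. This is correct and should be stated in the SAP.

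**Conclusion.** The point holds as an improvement to pre-specification and precision. The primary model depends on a condition that the plan does not define, and use of the baseline value of the primary outcome is not secured. The open covariate list means that the plan cannot be read as excluding T0.

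The size depends on assumptions. The documents give no T0-to-T3 correlation, no effect size and, apart from the eye-exam figure, no gap prevalence. The gain is negligible at weak correlation and useful at moderate correlation. It should not be quoted as the gain over the planned mixed model. Confidence is medium.

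**What to change.** Replace the conditional sentence in Section 6.0 with a named covariate set, fixed before any comparison by arm and used whatever the observed balance. Always include the T0 gap count, either as a covariate or as a response with a common baseline mean across arms. Name the 12-month arm contrast as the primary test, and state that its odds ratio is conditional on these covariates.

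First reconcile Section 2.0, which calls the trial cluster randomized, with Section 4.0, which describes permuted blocks and assignment of individual participants.
- If participants are randomized, an ordinal model of the 12-month count on arm, T0 and the fixed covariates is enough. A repeated-measures model is also possible, with patient-clustered robust standard errors.
- If clinics are randomized, the random effect or clustered errors must be at clinic level.

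The robust errors matter because of look-backs such as "no diabetes eye exam in the last 12 months". The 3- and 6-month windows overlap the baseline window and the 12-month window does not, which a patient intercept alone does not represent. In simulation, adding T0 to such a mixed model with model-based errors gave 7.0–8.6% type I error for the 12-month contrast. Robust errors gave 5.0–5.4% in the three settings checked (600–800 replicates; none at r = 0.20), and the 12-month-only model with T0 gave 4.5–5.9%. This is a caution about carrying out the fix, not an error in the plan.

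The cost is minor SAP wording and a conditional rather than marginal odds ratio. No new data or patients are needed.

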## **4.0 Enrollment/Randomization**

The study will be a pragmatic, parallel-design, randomized controlled trial (RCT). We will recruit patients into two study arms which will receive: (1) usual care (n=250) and (2) the patient portal intervention (n=250). Participants in Arm 1 (usual care) will have access to the standard version of MHAV. Participants in Arm 2 will be provided access to a version of MHAV embedded with the intervention. Participants in both arms will be told the purpose of the study is "to determine patients' satisfaction with MHAV among patients with diabetes."

Participants will be able to complete an electronic consent form and enroll online via Research Electronic Data Capture (REDCap™) version 5.0.8. The study coordinator will verify all eligibility criteria prior to randomization. The study procedures and risks will be explained to the participants and the consent form signed as per standard practice. The randomization sequence is generated by the research team biostatistician using a permuted block randomization scheme uploaded to REDCap. The randomized assignment for eligible participants is accessible to the study coordinator via REDCap.

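### Baseline diabetes distress is an imbalance-triggered covariate with no exemption for its own outcome model; the SAP should use the T0 score once, and always

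*Combined protocol and SAP*

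**What the plan says.** Table 2 (Section 5.0) lists diabetes distress as a continuous secondary outcome, measured by "Problem Areas in Diabetes Scale (PAID-5", with time points T0 to T3. The table footnote defines the labels: "T 0 = baseline, T 1 = 3-month follow-up". Section 5.0 confirms the collection schedule: "Study participants will complete questionnaires electronically via email using REDCap™ at four time points".

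Section 6.0 then says three things that meet in the distress model:

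- Adjustment is conditional: "If there is imbalance, we will control for baseline patient level covariates". No threshold or test for imbalance is given. The list that follows ends "education level, age, sex, health literacy, technology use, and diabetes distress".
- The model class for this type of outcome is fixed: "For continuous outcomes, a multivariate mixed effects regression model will be used". The response rows, the visit terms, any arm-by-visit term and the contrast to report are not stated.
- The rule carries over to the other endpoints with one exemption: "Similar models will be used for all the secondary outcomes except for HbA1c".

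Nothing removes distress from the covariate list when distress is itself the outcome.

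**The concern.** The PAID-5 score at T0 is both the first time point of an outcome and a candidate covariate for that outcome. An analyst could follow the SAP to the letter and fit T0 to T3 as response rows with the T0 score on the right-hand side. The T0 row is then regressed on itself. Its residual is artificially small, the pooled residual variance falls, and the follow-up arm differences look more precise than they are. The result would be too many false positives for distress.

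An analyst who takes only T1 to T3 as responses avoids that problem. That analyst would still adjust for the best available predictor of follow-up distress only when the arms happened to differ at baseline, by a criterion not fixed in advance. Precision already paid for by collecting T0 would be lost in every other case.

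**Working it through.** The plan gives no figure to reproduce: there is no power, SD or correlation for distress. The check therefore rests on stated assumptions.

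**Inputs.** From Section 4.0: "1) usual care (n=250) and (2) the patient portal intervention (n=250", so n = 250 per arm. From Table 2: four visits. Assumed: outcome SD 1 at every visit, constant correlation ρ between visits of 0.5, 0.6 or 0.7, no dropout, a random-intercept REML fit with arm-by-visit terms, and a two-sided 5% test of the T3 arm difference.

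**A. T0 as response row and as covariate.** The covariate is constant within a patient. With complete data its common slope is therefore the regression of the patient's four-visit mean on T0:

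b = (1 + 3ρ)/4

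- Residual variance of the T0 row: (1 − b)².
- Residual variance of each follow-up row: v = 1 + b² − 2bρ.
- The model assumes one common variance, about a = [(1 − b)² + 3v]/4.
- Model SE of the T3 difference ≈ √(2a/250); actual SE ≈ √(2v/250).
- Type I error ≈ 2 × [1 − Φ(1.96 × √(a/v))].

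| ρ | b | (1 − b)² | v | a | model SE | actual SE | ratio | type I error |
|---|---|---|---|---|---|---|---|---|
| 0.5 | 0.625 | 0.141 | 0.766 | 0.609 | 0.070 | 0.078 | 0.89 | 8.0% |
| 0.6 | 0.700 | 0.090 | 0.650 | 0.510 | 0.064 | 0.072 | 0.89 | 8.3% |
| 0.7 | 0.775 | 0.051 | 0.516 | 0.399 | 0.057 | 0.064 | 0.88 | 8.5% |

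Simulation agrees: the model SE is about 10 to 14% below the empirical SD, and rejection is about 7 to 9%. With T0 as covariate only and rows T1 to T3, rejection is about 4 to 6%.

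The T3 estimate is unbiased over all randomisations. Given an observed baseline difference d it is shifted by −(b − ρ)d = −(1 − ρ)d/4. At ρ = 0.6 and d = 0.18 SD this is −0.1 × 0.18 = −0.018 SD; simulation gave about −0.02 SD.

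**B. T0 not a response row.** Adjustment is then ordinary baseline adjustment, and the question is what is lost when it is not triggered.

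- Unadjusted T3 SE: √(2/250) = 0.089 SD.
- Adjusted T3 SE: √(2(1 − ρ²)/250) = 0.077, 0.072 and 0.064 SD for ρ = 0.5, 0.6 and 0.7.
- Reduction: 1 − √(1 − ρ²) = 13%, 20% and 29%.

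**C. The two proposed remedies.** In simulation at ρ = 0.6 with a true effect of 0.20 SD and a 0.18 SD baseline imbalance, T0 as covariate with rows T1 to T3 gave 0.200 (model SE 0.072, coverage 0.947). The model with T0 as response and arm means constrained equal at T0 gave 0.200 (model SE 0.072, coverage 0.945). They are practically the same.

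**The case against.** The strongest reply is that the documents never make T0 a response row. The Time Point column of Table 2 cannot settle it. HbA1c also carries T0 to T3 there, yet Section 6.0 models only its 12-month value. The 6-month care-gap count and the patient-initiated orders carry the same range. The column may simply describe when data are collected. This stands: a reader might infer that the plan prescribes distress on both sides of its own model, but it only permits it. With T1 to T3 as responses the adjustment is valid. Adjustment also enters only under imbalance, so the double use would not occur in every case.

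A reader might also attribute two further problems to the double use. Neither belongs to it:

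- **Change from T0 to T3.** This contrast is biased under chance imbalance, but its estimate and standard error are identical with and without the covariate. At ρ = 0.6 and 0.18 SD imbalance the bias was −0.074 SD in both fits.
- **One arm effect pooled over T0 to T3.** This is diluted because one of the four rows precedes treatment. A true 0.20 SD came out as 0.150 with the covariate and 0.148 to 0.153 without it. With the covariate, the standard error shrinks in proportion and the test keeps its level.

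The size of the remaining harm also depends on the assumed covariance. In a case where correlation falls with time, the double use rejected 12.0%, but the single-use random-intercept model also exceeded its level, at 7.3%. Using T0 once does not cure a misspecified covariance.

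None of this answers the two residual points: the SAP leaves the double use open, and under the harmless reading it still makes a useful adjustment depend on an undefined trigger.

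**Conclusion.** The point holds as a gap in specification with a consequence under either reading. If T0 is a response row and the covariate is triggered, the T3 arm difference for distress has a model standard error about 10 to 14% too small and a type I error of about 7 to 9% instead of 5%. If T0 is not a response row, inference is valid, but the T3 standard error is about 0.09 SD whenever adjustment is not triggered, against 0.064 to 0.077 SD with adjustment.

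These sizes rest on constant visit correlations of 0.5 to 0.7, complete data, a random-intercept model and the T3 arm difference as the contrast. None of these is stated in the documents. The documents do not support saying that the double use is planned or certain. The scope is one secondary outcome, and the primary analysis of care gaps is untouched.

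**What to change.** Add to Section 6.0, for the diabetes distress outcome only:

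- T0 distress is used once, and always, whether or not the arms differ at baseline. Either it is a covariate with T1, T2 and T3 as the only response rows, or it is a response row with arm means constrained equal at T0 and distress removed from that model's covariate list.
- The model includes arm, visit and arm-by-visit, and the reported effect is the arm difference at T3.

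Baseline distress can stay on the covariate list for the other outcomes.

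The cost is a sentence or two of text. No new data are needed, because the T0 questionnaire is already scheduled. One downside: with T1 to T3 as response rows, a patient who returns only the T0 questionnaire contributes nothing unless the follow-up scores are imputed. Section 6.0 already allows for multiple imputation, and the text should say whether it applies here.
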